- An investigator or research coordinator will contact the invited candidates by phone one week before the scheduled procedure. The study's purpose, intervention, and consent process will be discussed during this call, which will be documented in the patient's chart.
- Patients interested in participating will receive the consent form through DocuSign, with instructions on how to complete it online.
- A follow-up phone call will be made 1-2 days later to answer any questions the patient may have.

Rationale for Electronic Consent (E-Consent)

- Many procedures are scheduled through open access, meaning the patient is scheduled by a provider other than the one performing the procedure, often from a different department. In these cases, the patient may not meet the performing physician until the day of the procedure.
- E-consent allows patients more time to consider participation without the pressure of deciding on the day of the procedure.

Sample size calculations

Assuming a 93% success rate in both arms and no true difference between colonoscope types, we aim to test statistical equivalence using a two-sided type I error of 0.05 and power of 80%. A 10% margin (± 0.10) in success rate is considered clinically acceptable and forms the basis for the equivalence hypothesis:

$$H_0: |p_1 - p_2| \geq 0.1$$

$$H_1: |p_1 - p_2| < 0.1$$

Based on these assumptions, a fixed sample size of 112 participants per group (total N = 224) is required. To preserve operating characteristics under the group sequential framework, the maximum sample size is inflated by an estimated factor of 1.082, yielding a maximum of 122 participants per group (total N = 244). The interim analysis will occur after enrollment of 122 participants (61 per group). (Group Sequential Methods with Applications to Clinical Trials by Jennison and Turnbull (pages 149–150) [2].

Study Variables

Date of birth, gender, race, BMI, previous pelvic\abdominal surgery, diverticulosis, colon prep (adequate- inadequate), type of colonoscopy, insertion time, cecum and terminal ileum intubation success, and procedure time. Please refer to the data collection sheet for details of the variables above.

Data Analysis

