All statistical analyses will be conducted by a statistician from the Cleveland Clinic's Quantitative Health Sciences (CCF QHS) team, following the intention-to-treat (ITT) principle. This means that all randomized patients who receive one of the study interventions will be included in the primary analysis.

Baseline characteristics will be assessed for balance using standardized mean differences (SMDs), with a value less than 0.10 (absolute) indicating acceptable balance.

Missing data in baseline variables are expected to be minimal. If more than 5% of data are missing for any key variable, multiple imputation methods will be employed.

The primary outcome—successful completion of the colonoscopy (Yes/No)—will be analyzed as a binary endpoint. The effect of colonoscope type (adult vs. pediatric) will be evaluated using the Two One-Sided Tests (TOST) procedure, with a pre-specified equivalence margin of $\pm 10\%$. The absolute risk difference of 10% will also be translated into corresponding thresholds for odds ratios (OR = 2.72 or OR = 0.36) and relative risks (RR = 1.12 or RR = 0.893). Both unadjusted and adjusted logistic regression models, incorporating pre-specified covariates, will be used to estimate treatment

effects. Results will be presented as risk differences, relative risks, and odds ratios, with 95% confidence intervals derived via the g-computation method. Equivalence will be declared if the full confidence interval lies entirely within the specified equivalence range on each metric.

A per-protocol analysis will be conducted as a sensitivity analysis if there is substantial non-compliance. Additional sensitivity analyses will be considered to address missing data in outcome variables.

Secondary outcomes including cecal intubation rate (CIR), terminal ileum intubation rate (TIIR), insertion time (IT), use of ancillary maneuvers, withdrawal time, are considered independent of the primary outcome. Categorical secondary outcomes will be compared using chi-squared or Fisher's exact tests, while continuous variables will be analyzed using two-sample t-tests or Wilcoxon rank-sum tests as appropriate. Regression models adjusting for pre-specified covariates will also be considered.

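### The equivalence rule adds odds-ratio and relative-risk limits to a trial sized on the risk difference only; read as a joint rule, power at the planning assumptions is about 9%, not 80%

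*Combined protocol and SAP*

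**What the plan says.** Sample size calculations puts both hypotheses on the absolute difference in success rates and takes that as the clinical standard: "A 10% margin (± 0.10) in success rate is considered clinically acceptable and forms the basis for the equivalence hypothesis". The planning assumption is "Assuming a 93% success rate in both arms and no true difference between colonoscope types", with a "two-sided type I error of 0.05 and power of 80" per cent. The result is 112 per group, raised to a maximum of 122 for the group sequential design.

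Data Analysis specifies TOST with the ±10% margin and also converts the margin into "corresponding thresholds for odds ratios (OR = 2.72 or OR = 0.36) and relative risks (RR = 1.12 or RR = 0.893"). Unadjusted and adjusted logistic models are to give all three measures with 95% g-computation intervals. The rule then reads: "Equivalence will be declared if the full confidence interval lies entirely within the specified equivalence range on each metric".

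No measure is named as the decisive one, and no power is given for the OR or RR conditions.

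**The concern.** The trial is powered for one criterion, but its success rule names three. Limits that correspond at one pair of rates (93% v 83%) are not equally hard to meet. With success near 93%, each arm has only 8 or 9 failures, and the OR is estimated from those failures. Its interval can be almost as wide as the permitted range even when the two arms give identical results.

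If the rule is followed as most naturally read, two truly identical scopes would probably not be declared equivalent, although the risk difference was estimated well within 10 points. The stated 80% power would then not describe the rule that decides the trial.

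**Working it through.** **Inputs.** From Sample size calculations: success p = 0.93 in both arms, margin m = 0.10, alpha 0.05, power 80%, 112 per group (maximum 122). From Data Analysis: OR limits 0.36 and 2.72, RR limits 0.893 and 1.12, 95% intervals.

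**1. The plan's sample size reproduces, on the risk difference alone.** n = 2p(1−p)(z₁₋α + z₁₋β/₂)²/m².
- α = 0.05 per one-sided test: 2 × 0.93 × 0.07 × (1.645 + 1.282)²/0.01 = 111.5, so 112. Then 112 × 1.082 = 121.2, so 122.
- α = 0.025 per test (a 95% interval): 2 × 0.93 × 0.07 × (1.960 + 1.282)²/0.01 = 136.8, so 137.

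The planned size therefore matches one-sided 0.05 tests, that is, a 90% interval.

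**2. The limits come from 93% v 83%.** OR = (0.93/0.07)/(0.83/0.17) = 2.721, inverse 0.367. RR = 0.93/0.83 = 1.120, inverse 0.892. The printed 0.36 is slightly off its inverse, but three-measure power is 8.8% with either value.

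**3. Precision of the OR.** SE(log OR) = √[2/(122 × 0.93 × 0.07)] = 0.502. The 95% half-width is 1.96 × 0.502 = 0.98, against ln 2.72 = 1.00. An interval centred on OR = 1 nearly fills the range.

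**4. A tie at 114/122 in each arm (8 failures each).**
- OR: SE = √(2/114 + 2/8) = 0.517; exp(±1.96 × 0.517) gives 0.363 to 2.756. The upper limit exceeds 2.72, so it fails.
- Risk difference: 1.96 × √[2 × (114/122) × (8/122)/122] = 0.062, or ±6.2 points. It passes easily.

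With 9 failures in each arm, SE = √(2/113 + 2/9) = 0.490 and the upper limit is 2.61, which passes.

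**5. Power at 122 per group, p = 0.93 in both arms.** Every pair of outcomes from two Binomial(122, 0.93) arms was enumerated, with unadjusted Wald intervals (log scale for RR and OR) and one final look.

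| Criterion | 95% interval | 90% interval |
|---|---|---|
| Risk difference alone | 72.1% | 84.0% |
| RR alone | 78.3% | 87.2% |
| Risk difference and RR | 72.1% | 84.0% |
| OR alone | 8.8% | 28.1% |
| All three | 8.8% | 28.0% |

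Adding the RR limit costs nothing at 93%; the OR limit accounts for the fall. A 0.5 continuity correction gives 11.1% for all three with 95% intervals; a natural-scale delta-method OR interval gives essentially 0%. The two-look equivalence bounds applied to the risk difference, ignoring futility, give 72.3% by simulation.

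**6. Other true success rates, identical arms, 95% intervals.**

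| True rate | Risk difference alone | Risk difference and RR | All three |
|---|---|---|---|
| 80% | 4.0% | 1.0% | 1.0% |
| 85% | 18.4% | 15.1% | 14.7% |
| 88% | 34.7% | 33.9% | 27.8% |
| 90% | 48.1% | 48.0% | 26.5% |
| 93% | 72.1% | 72.1% | 8.8% |
| 95% | 87.9% | 87.9% | 1.1% |

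Three-measure power peaks at about 28% near 88% success.

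**7. Size needed for the OR limit.** The normal approximation gives about 316 per group for 80% power with 95% intervals. Exact enumeration gives 77.6% at 320 and 79.5 to 79.8% at 330, and passes 80% by about 335 per group.

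**The case against.** The strongest reply is that OR and RR are subordinate. The hypotheses are on the risk difference, TOST is specified with the ±10% margin, the other limits are introduced as translations of it, and nowhere does the plan say that the three must hold jointly. The rule might mean a separate declaration for each measure. That reading is possible, so a reader should not treat the joint requirement as beyond doubt. It does not rescue the rule: no measure would then carry the primary conclusion, and the 114/122 tie would be equivalent on the risk difference but not on the OR.

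Other stronger inferences are not supported:
- *Better performance always lowers the chance of success.* Three-measure power rises to about 88% success and falls only above that. At 85% or below the OR limit adds little.
- *The OR limit explains the whole gap from 80% to 9%.* Part is separate: using a 95% rather than a 90% interval lowers risk-difference power at 122 per group from 84% to 72%.
- *The rule risks false claims of equivalence.* Extra conditions can only make a declaration harder. The harm is an inconclusive trial.

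It is also fair to object that the plan specifies g-computation intervals, from adjusted as well as unadjusted models, and an interim look. The exact 8.8% depends on the interval method; the alternatives tried range from essentially 0% to 11%, so the direction stands.

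**Conclusion.** The concern holds. The success rule does not match the hypothesis and sample size. On its most natural reading, power at the plan's own assumptions is about 9%, against about 72% for the risk difference alone (28% against 84% with 90% intervals). The size of the loss is specific to success rates near or above the planned 93%, but three-measure power does not exceed roughly 28 to 29% at any rate examined from 80% to 97%. On the alternative reading the fault is that no decisive measure is named.

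These figures assume identical arms, 122 analysed per group, unadjusted Wald intervals in place of g-computation intervals, and a single final look with no futility stop. The sample size of 112 is not itself miscalculated: it reproduces for a risk-difference test at one-sided 0.05.

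**What to change.** In Data Analysis, replace the decision sentence with one stating that equivalence is declared if the confidence interval for the risk difference lies entirely within ±0.10, and that RR and OR are reported descriptively with no role in the decision.

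State the confidence level in the same sentence and make it agree with the sample-size alpha. The 112 per group corresponds to one-sided 0.05 tests, hence a 90% interval. If the 95% interval is kept, restate the power as about 72%. The final critical value in the Interim analysis table (1.959964) is that of a 95% interval, so it must be reconciled with whichever level is chosen. Say also whether the unadjusted or the adjusted estimate decides.

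The cost is a wording amendment, with no extra patients or data. Because it relaxes the primary decision rule, it must be fixed and dated before anyone sees outcome data, including the interim. Keeping the OR limit as a requirement would instead need about 335 per group.

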Randomized controlled trial comparing adult to pediatric colonoscope in obese patients.

NCT 06776913

Randomized controlled trial comparing adult to pediatric colonoscope in obese patients.

Corresponding author:

[name]

Email: [contact]

Address: [name]

Principal Investigator:

[name]

Email: [contact]

Address: [name]

Background

A colonoscopy is a routine procedure performed daily for various purposes, including colon cancer screening. Over time, colonoscopes have evolved and now come in different sizes, diameters, and flexibility levels. The choice of colonoscope typically depends on the endoscopist's preference, and anecdotal experience, with all types of instruments considered standard practice.

Several patient characteristics can make routine colonoscopy more challenging, such as diverticulosis and a history of previous surgeries, especially in the pelvic area. These challenging cases might influence the provider to choose one instrument over another, although there is a general lack of evidence demonstrating the superiority of specific colonoscopes in certain situations.

Obesity is one of the challenges encountered during routine colonoscopy. A retrospective study showed no difference in the performance of adult and pediatric scopes when matching the population's BMI. However, providers tend to choose adult scopes for higher BMI patients in unmatched populations. We designed this study to evaluate if adult and pediatric colonoscopes perform differently in obese patients, which both are considered standard practice in the study population.

Study objective.

The objective of this equivalence trial is to evaluate whether pediatric and adult colonoscopes achieve similar success rates in obese patients undergoing colonoscopy. Patients will be randomly assigned in a 1:1 ratio. The primary endpoint is the success rate of colonoscopy completion without switching instruments (defined in the main protocol).

Study hypothesis.

There is no significant difference between adult and pediatric colonoscopes in the evaluation of obese patients.

Study design.

Prospective randomized single-blinded Equivalence trial

- ➔ The patient is blinded regarding the instruments used.
- ➔ The endoscopist is not blinded. blinding is not feasible as the endoscopist would recognize the different instrument dimensions before the procedure.

Primary outcome

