Repeatedly measured outcomes will be analyzed using mixed-effects models, with study group and time point included as fixed effects, and subject ID as a random effect to account for within-subject correlation. This approach is robust to data that are missing at random (MAR) or missing completely at random (MCAR).

Data Security

Data, including patient information and consent, will be stored electronically in the Redcap system\DocuSign which is password-protected and on the secure Cleveland Clinic network. If physical paper sheets were used, the physical paper sheets' information would be transferred to Redcap and shredded on the day of data gathering.

Interim analysis

A group sequential design with a single interim analysis at 50% enrollment is proposed. This design allows early trial termination for either efficacy (equivalence) or futility (non-equivalence), while preserving the overall type I error ($\alpha = 0.05$) and power ($1 - \beta = 0.80$).

The design employs Hwang-Shih-DeCani gamma error spending functions [1]:

- Type I error: $\gamma = -4$ (O'Brien-Fleming-like)
- Type II error: $\gamma = 1$ (Pocock-like)

Analysis Stage	Type I Error Spending (Cumulative)	Type II Error Spending (Cumulative)
Interim (50%)	0.00596	0.124
Final (100%)	0.05	0.2

A non-binding futility boundary is used. Z-stopping-boundaries are shown below.

Analysis Stage	Equivalence		Non-equivalence	
	upper	lower	upper	lower
Interim (50%)	2.749966	-2.749966	1.152821	-1.152821
Final (100%)	1.959964	-1.959964	1.959964	-1.959964

Possible Harm to Subjects

Both study arms are considered standard treatment, and no anticipated harm is related to the study.

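### The interim boundary table does not follow its stated spending function, uses a different alpha scale from the sample size, and makes an early equivalence stop unlikely at the planned 93% success rate

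*Combined protocol and SAP*

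**What the plan says.** In the Combined protocol and SAP, Sample size calculations sets the assumptions: "Assuming a 93% success rate in both arms and no true difference between colonoscope types", "using a two-sided type I error of 0.05 and power of 80" percent, and "A 10% margin (± 0.10) in success rate is considered clinically acceptable". It derives 112 per group for a fixed design, inflates by 1.082 to 122 per group, and fixes the timing of the look: "The interim analysis will occur after enrollment of 122 participants (61 per group").

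Data Analysis names the "Two One-Sided Tests (TOST) procedure, with a pre-specified equivalence margin" of 10 percentage points, and bases the decision on effect estimates "with 95% confidence intervals derived via the g-computation method".

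Interim analysis says: "This design allows early trial termination for either efficacy (equivalence) or futility (non-equivalence"), with overall alpha 0.05 and power 0.80 preserved. It specifies Hwang-Shih-DeCani spending (gamma −4 for type I error, gamma 1 for type II), cumulative type I spends of 0.00596 and 0.05, and a non-binding futility boundary. The equivalence boundaries are ±2.749966 at the interim and ±1.959964 at the end. No probability of stopping early is given.

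**The concern.** Once some alpha has been spent at an interim look, the final critical value has to exceed the fixed-sample quantile. A final boundary equal to that quantile suggests that the table was not solved from the spending function printed above it. The value also belongs to a 0.025-per-side test, which may not be the test that the sample size was built for.

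Separately, a boundary of 2.75 looks high for 61 per group, so the early equivalence stop may offer little.

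Three things are at stake: the critical value that the statistician will apply at the end, the power that the trial actually has, and what those running it can expect from the interim look.

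**Working it through.** **Inputs.** Success 0.93 in both arms, margin 0.10, 112, 122 and 61 per group (Sample size calculations); 1:1 allocation (Study objective); two one-sided tests and 95% intervals (Data Analysis); spends, boundaries and non-binding futility (Interim analysis). I assume that the boundaries apply to the two statistics (d + 0.10)/SE and (0.10 − d)/SE, both of which must pass. No other reading fits the stated hypotheses.

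**1. The plan's own figures.**
- Fixed sample size: n = 2p(1−p)(z₁₋α + z₁₋β/₂)²/margin². With α = 0.05 per one-sided test: 0.1302 × (1.645 + 1.282)²/0.01 = 111.5, so 112. With 0.025 per side: 0.1302 × (1.960 + 1.282)²/0.01 = 136.8, so 137. Only the first matches.
- Maximum: 112 × 1.082 = 121.2, so 122.
- Interim type I spend: 0.05 × (1 − e²)/(1 − e⁴) = 0.00596.
- Interim boundary: z(1 − 0.00596/2) = 2.74997. Final boundary: z(1 − 0.05/2) = 1.959964.
- The interim futility value has the same form: the type II spend is 0.1245, and z(1 − 0.1245) = 1.1528.

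The sample size therefore uses 0.05 per one-sided test, while both equivalence boundaries use 0.025 per side.

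**2. Final boundary implied by the spending function.** The interim and final statistics have correlation √0.5. Non-binding futility cannot be used to lower the efficacy boundary. Solving P(Z₁ ≥ 2.75 or Z₂ ≥ c) = 0.025 gives c = 1.981. With c = 1.96 the probability is 0.0262. On the 0.05-per-test scale, the same spending function gives 2.514 at the interim and 1.664 at the end.

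**3. Final-look power at 122 per group.** SE = √(2 × 0.93 × 0.07/122) = 0.0327, so 0.10/SE = 3.061. Power = 2Φ(3.061 − c) − 1, before any loss from stopping for futility:

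| Final boundary c | Power |
|---|---|
| 1.960 | 72.9% |
| 1.981 | 72.0% |
| 1.664 | 83.8% |

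Exact enumeration with an unpooled Wald SE gives 72.1% at both 1.960 and 1.981, and 82.8% at 1.664.

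**4. Chance of an early equivalence stop at 61 per group.** At the planned variance SE = √(2 × 0.93 × 0.07/61) = 0.0462. Even with an observed difference of zero, Z is at most 0.10/0.0462 = 2.16, below both 2.75 and 2.514. At 93%, a Z of 2.75 first becomes reachable at 2.75² × 0.1302/0.01 = 98.5, that is 99 per group, or 81% of 122.

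With an estimated Wald SE, enumerating all outcomes shows that 2.75 is passed when each arm has at most 2 failures; 61 × 0.07 = 4.3 are expected. At 93%, P(at most 2 failures in an arm) = 0.191, and 0.191² = 0.036. With 2.514 the outcome of 3 failures in each arm is added. The exact chances are:

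| True success, both arms | 2.75 | 2.514 |
|---|---|---|
| 90% | 0.2% | 0.9% |
| 93% | 3.6% | 7.0% |
| 95% | 16.5% | 21.8% |
| 96% | 31.0% | 35.7% |

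With a restricted-likelihood score SE, the chance at 93% is 0% with 2.75 and 0.01% with 2.514.

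**The case against.** Three stronger readings are tempting, and the documents support none of them.

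- **The interim equivalence boundary cannot be met.** That is true only at the planned variance or with a score SE. With a Wald SE it is met whenever neither arm has more than 2 failures, including unequal results such as 0 against 2. The chance is material if true success is 95% or more. The plan openly chooses an O'Brien-Fleming-like spend, which is conservative early, and promises no particular stopping probability. A low chance at 93% is partly a design preference, though readers should be told of it.
- **The type I error is inflated to 0.0524.** That figure adds the two sides. When the true difference sits at one margin, only that one-sided null is at risk, so the tabled boundaries imply about 0.026. This is below 0.05 if alpha means 0.05 per one-sided test. Even 0.0262 is a ceiling, because an interim stop needs both tests to pass. In the exact Wald calculation, 1.960 and 1.981 give the same probability of declaring equivalence, to four decimals, at every rate tried from 90% to 98%.
- **Dropping the interim equivalence stop makes 1.96 right.** It would remove the spending mismatch at 0.025 per side. It would not make 1.96 consistent with a sample size built on 1.645.

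What stands is that the printed table is not the output of the stated spending function, and that its alpha scale differs from the one behind the sample size.

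**Conclusion.** The point holds in limited form. The final equivalence boundary should be 1.981 rather than 1.959964 if 0.025 per side is intended, a shift of 0.02 with negligible effect on type I error. The mismatch of scale matters more: under the tabled boundaries and the 95% interval rule, final-look power at 122 per group is about 73%, not the stated 80%. At the planned 93%, early stopping for equivalence has about a 4% chance, so the look serves almost only for futility unless true success is higher.

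The power and boundary figures rest on normal theory, equal true rates and an information fraction of 0.5. The stopping chances rest on a Wald SE for the risk difference. The plan does not say which SE the boundaries use, and it also requires equivalence on the relative risk and odds ratio, which is not modelled here.

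**What to change.** Choose one alpha scale before any interim comparison is made, and recompute the whole boundary table from the stated spending functions, including the futility column and the 1.082 inflation. Two options are consistent:

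- **0.05 per one-sided test.** Boundaries 2.514 and 1.664, with the 95% interval rule in Data Analysis replaced by a matching 90% rule (final multiplier 1.664) and the two-sided 0.05 wording corrected. Final-look power at 122 per group is about 84%, before any futility loss.
- **0.025 per side.** Boundaries 2.750 and 1.981, with power restated as about 72%. To keep 80% the sample would have to grow, starting from 137 per group before inflation.

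Under either option, name the SE that the boundaries use. State the chance of an early equivalence stop at 93% (about 4% with 2.75, 7% with 2.514, Wald SE) and across a range such as 90% to 96%. Dropping the interim equivalence stop is optional; at exactly 93% it gives up only that 4% to 7% chance, but more if true success is higher, and the alpha scale must still be settled.

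The cost is a recalculation, a revised table and edits to three sections. The first option needs no more participants but accepts a less strict decision rule. The second keeps the stricter rule and accepts lower power or a larger trial.

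### The interim non-equivalence boundary of ±1.152821 leaves out the drift; at the planning values about 30% of truly equivalent trials would cross it, against the 12.4% stated

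*Combined protocol and SAP*

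**What the plan says.** The Interim analysis section sets one look at 50% enrolment, allows stopping for equivalence or non-equivalence, and claims that overall alpha of 0.05 and power of 0.80 are both kept. Type II error is spent by a Hwang-Shih-DeCani function with gamma = 1, giving a cumulative 0.124 at the interim and 0.2 at the end. Of the stopping rule it says "A non-binding futility boundary is used. Z-stopping-boundaries are shown below". The interim row gives ±2.749966 for equivalence and ±1.152821 for non-equivalence; both final entries are ±1.959964. No formula for Z is given.

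The planning values are in Sample size calculations: "Assuming a 93% success rate in both arms and no true difference between colonoscope types", "using a two-sided type I error of 0.05 and power of 80" per cent, and "A 10% margin (± 0.10) in success rate is considered clinically acceptable". The interim comes at 61 per group and the maximum is 122 per group. Data Analysis says that the primary outcome is "evaluated using the Two One-Sided Tests (TOST) procedure".

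**The concern.** Type II error is the chance of failing to show equivalence when the scopes are equal. A boundary that spends a given amount of it must therefore be set from the distribution of the test statistic under equality. For the two TOST statistics that distribution is not centred at zero: its mean (the drift) is the margin divided by the standard error. The tabled entry depends only on the amount spent. It would be the same for any margin, success rate or interim sample size, so it cannot in general deliver the 0.124 printed beside it.

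At stake is the decision at 122 patients. A boundary set too high labels as non-equivalent many trials in which the scopes perform alike, and a team that follows it loses power that the section says is kept.

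**Working it through.** **Inputs.** Success p = 0.93 in both arms, margin 0.10, 61 per group at the interim and 122 at the end (Sample size calculations); total type II error 0.2, gamma = 1, interim boundary 1.152821, equivalence boundaries 2.749966 and 1.959964 (Interim analysis).

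**1. Reproduce the table.** Spending at half information is 0.2 × (1 − e^−0.5)/(1 − e^−1) = 0.124492, printed as 0.124. The upper normal quantile of 0.124492 is 1.152821, which is the tabled entry to every printed digit.

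**2. Drift at the interim.** SE = √(2 × 0.93 × 0.07/61) = 0.04620. Drift = 0.10/0.04620 = 2.1645.

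**3. Crossing probability under equality.** Write d for the observed difference, Z_L = (d + 0.10)/SE and Z_U = (d − 0.10)/SE. The rule is crossed if Z_L < 1.152821 or Z_U > −1.152821, that is, if |d| > 0.10 − 1.152821 × 0.04620 = 0.0467.

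- Normal approximation: 2 × Φ(1.152821 − 2.1645) = 2 × 0.1558 = 31.2%.
- Exact binomial enumeration, 61 per arm, estimated SE: 30.3%.
- Stated: 12.4%.

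**4. Dependence on the success rate** (no true difference):

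| Success in both arms | Normal | Binomial |
|---|---|---|
| 90% | 49% | 47% |
| 93% | 31% | 30% |
| 95% | 17% | 17% |
| 97% | 4% | 6.5% |

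**5. Boundary with the drift.** Splitting 0.1245 equally over the two sides uses the quantile 1.5362, so the boundary is 2.1645 − 1.5362 = 0.628. It is crossed when |d| > 0.10 − 0.628 × 0.04620 = 0.071. By construction this spends 12.4% in the normal approximation; binomial enumeration gives 11.5%.

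**6. Power at 122 per group, 93% in both arms, tabled equivalence boundaries.** Final drift = 0.10/√(2 × 0.93 × 0.07/122) = 3.061. With futility ignored, the normal approximation gives 2 × Φ(3.061 − 1.960) − 1 = 72.9%; binomial simulation gives about 72%.

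| Interim futility rule | Power |
|---|---|
| Ignored | about 72% |
| 0.628, followed | about 69% |
| 1.152821, followed | about 57% |

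**7. Where the rest of the shortfall lies.** The fixed-design formula is n = 2p(1 − p)(z + 1.2816)²/0.10², with z the one-sided quantile for alpha and 1.2816 the quantile for half of the 0.2. At 0.05 per side it gives 111.5, hence the plan's 112; at 0.025 per side it gives 137. The tabled 1.959964 is the 0.025-per-side quantile. With equivalence boundaries at 0.05 per side (2.514 and 1.645), power by binomial simulation is about 64% when 1.152821 is followed and about 79% when 0.628 is followed.

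**The case against.** *Futility is non-binding.* This stands as a limit on the wording. A reader might infer that the plan will stop about 30% of truly equivalent trials. The documents do not support that: such trials cross the boundary, and stop only if the team follows it. But a non-binding rule protects the type I error when it is overridden; it does not protect power when it is followed, and it does not make the boundary match its stated spend. Type I error is not in question here, because extra futility stops can only lower it.

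*Z is undefined, so the TOST scale is an inference.* True. If Z is d/SE, the two-sided crossing probability under equality is 2 × 0.1245 = 24.9%, still twice the stated figure. Only counting one tail gives 12.4%, and the table prints both an upper and a lower bound. The centred reading also fits the table poorly: equivalence would be declared for small |Z|, yet the equivalence entry (2.75) lies farther from zero than the non-equivalence entry (1.15), so the two regions would overlap.

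*The figure rests on 93%.* It does. At 97% the crossing rate falls below the stated spend. But 93% is the plan's own design value.

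*The loss of 80% power has another cause.* A reader might infer that this entry alone loses the claimed power, or that correcting it alone restores it. Neither follows. Power is already about 72% with futility ignored, because the equivalence boundaries use 0.025 per side.

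**Conclusion.** The interim non-equivalence entry is wrong as written: it does not deliver the type II error tabled beside it on either two-sided reading of Z. On the TOST scale, at 93% in both arms and 61 per group, about 30–31% of truly equivalent trials would cross it, against 12.4%. Its own share of the power loss, if the boundary is followed and the tabled equivalence boundaries are kept, is roughly the drop from 69% to 57%. Most of the gap between 69% and 80% is a separate mismatch between the equivalence boundaries and the sample size. These sizes assume the planning success rate, no true difference, an equal split of the spend over two sides, and full enrolment to 61 and 122 per group. The identity in step 1 needs none of these assumptions. The point should be settled before the interim look.

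**What to change.** In the Interim analysis section:

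1. Define Z_L = (d + 0.10)/SE and Z_U = (d − 0.10)/SE, state how SE is estimated, and state which statistic each tabled bound applies to.
2. Replace the interim non-equivalence entry with a drift-based boundary that spends 0.1245 over both sides. As an illustration at the planning values, the rule would be to stop if Z_L < 0.63 or Z_U > −0.63, an observed difference beyond about 7.1 points.
3. Derive it jointly with the equivalence boundaries and the 1.082 inflation factor. The per-side alpha, the futility boundary and the maximum sample size depend on one another, so 0.63 is provisional until they agree.
4. Say whether the boundary is a fixed Z or is recomputed from the interim SE. The two differ: a fixed 0.628 would be crossed with probability 2 × Φ(0.628 − 1.841) = 22.5% at 90% success and 2 × Φ(0.628 − 2.534) = 5.7% at 95%.
5. Restate the power that the final table delivers, with the futility boundary followed and ignored.

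The work is a recalculated table and some wording; the sample size changes only if the joint derivation requires it. The downside is fewer early stops when the scopes really differ. At a true 10-point difference (93% against 83%, binomial), futility stops at the interim fall from about 87% to about 73%.
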